# 4.0 Study Endpoints

- 4.1 To perform a prospective cohort trial to establish optimal timing to test for SOS using SWE.
- 4.2 Determine if SWE can provide earlier SOS diagnosis compared to clinical criteria.
- 4.3 Quantify the difference in SWE values between SOS patient who would benefit from drug treatment versus those who do well with supportive care.
- 4.4 Quantify relative ability to CEUS parameters versus grayscale and Doppler ultrasound.

# 5.0 Study Intervention/Investigational Agent

5.1 Lumason (sulfur hexafluoride lipid-type A microspheres) for injectable suspension is used to prepare the ultrasound contrast agent. The single use kit contains the following three items:

- One clear glass 10mL vial containing 25mg of lyophilized powder lipidtype A, 60.7 mg of sulfur hexafluoride gas and capped with a blue flip-cap
- One prefilled syringe containing 5 mL Sodium Chloride 0.9% Injection, USP (Diluent)
- One Mini-Spike

Each vial is formulated as a 25 mg sterile, pyrogen-free lyophilized powder containing 24.56 mg of polyethylene glycol 4000, 0.19 mg of distearoylphosphatidyl-choline (DSPC), 0.19 mg of dipalmitoylphosphatidylglycerol sodium (DPPG-Na) and 0.04 mg of palmitic acid. The headspace of each vial contains 6.07 mg/mL ( $\pm 2$  %) sulfur hexafluoride, SF6, or 60.7 mg per vial.

Each prefilled syringe with 5 mL of diluent 0.9% Sodium Chloride Injection is sterile, nonpyrogenic, preservative free containing 9 mg sodium chloride per mL.

Upon reconstitution with 5mL diluent, Lumason is a milky white, homogeneous suspension containing sulfur hexafluoride lipid-type A microspheres. The suspension is isotonic and has a pH of 4.5 to 7.5; it is only for intravenous administration.

The sulfur hexafluoride lipid microspheres are composed of SF6 gas in the core surrounded by an outer shell monolayer of phospholipids consisting DSPC and DPPG-Na with palmitic acid as a stabilizer. Sulfur hexafluoride has a molecular weight of 145.9. Each milliliter of reconstituted Lumason suspension contains 1.5 to 5.6 x108 microspheres, 68 mcg SF6 (12 mcL), 0.038 mg DSPC, 0.038 mg DPPG-Na, 4.91 mg polyethylene glycol 4000 and 0.008 mg palmitic acid. The sulfur hexafluoride associated with the microspheres suspension is 45 mcg/mL. Fifteen to twenty three percent of the total lipids in the suspension are associated with the microspheres. The sulfur hexafluoride lipid microsphere characteristics are listed in Table 2:

Microsphere Characteristics		
Mean diameter range	1.5 – 2.5 μm	
Percent of microspheres	$\leq 10 \ \mu m \geq 99\%$	
Upper size limit	$100.0\% \le 20 \ \mu m$	

# 6.0 **Procedures Involved**

6.1 Single-site prospective cohort study to evaluate grayscale US, Doppler US, CEUS and SWE examinations in BMT patients younger than 21 years. Patients will be identified by the study team during a weekly conference that involves the study team and the Children's Mercy BMT team. All eligible patients will be approached for written informed consent by a member of the study team and if they consent, then they will be enrolled into the study prior to the start of their conditioning regimen.

### Ultrasound Examinations and Timeline

After enrollment and within two weeks prior to starting their conditioning regimen, a limited abdominal US with Doppler measurements of the hepatic arteries, hepatic and portal veins, contrast enhanced ultrasound (CEUS) of the liver, as well as SWE will be performed.

Subjects will be undergo US examinations based on disease course as outlined below:

- 1. All Patients: Patients will undergo limited abdominal US with Doppler, CEUS and SWE once a week upon admission for conditioning until the patient day +30 BMT or discharge, whichever comes first.
- 2. Inpatient SOS: patients will undergo limited abdominal US with Doppler, CEUS and SWE once a week upon admission for conditioning until resolution of SOS.
- 3. Late Onset SOS: patients will undergo limited abdominal US with Doppler, CEUS and SWE once a week upon admission for conditioning until resolution of SOS.

The clinical team will order US, CEUS and SWE exams when patients have clinical suspicion for SOS and we will include these exams in our analysis. All imaging will be performed using GE Logiq E9 US machines by dedicated pediatric sonographers and interpreted by board-certified pediatric radiologists. Twelve shear wave velocity measurements will be taken 2-3 cm below the liver capsule at the mid-clavicular line in the right hepatic lobe and another 12 will be taken in the left hepatic lobe near midline

avoiding areas of vasculature (24). By necessity, the sonographer and interpreting radiologist will not be blinded to the clinical status of the patient. US and clinical data will be collected weekly and managed using REDCap electronic data capture tools hosted at Children's Mercy Hospital (25).

	ALL PATIENTS		INPATIENT SOS	LATE ONSET SOS
	Prior to	Start of Conditioning	Through	Through Resolution of
	Conditioning	through Day +30	Resolution of SOS	SOS
	Screening	Once per Week	Once per Week	Once per Week
Limited Abdomen and Limited Abdominal Doppler Ultrasound	X	Х	Х	X
Contrast Enhanced Ultrasound	X	X	X	X
Ultrasound Elastography	X	X	X	X

Table 3. Ultrasound Timeline

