# 2.0 Objectives

- 2.1 Our central hypothesis is that SWE changes will precede clinical and conventional ultrasound diagnostic criteria for SOS. We would like to perform a prospective cohort trial to establish optimal timing to test for SOS using SWE
- 2.2 Determine if SWE can provide earlier SOS diagnosis compared to clinical criteria.
- 2.3 Quantify the difference in SWE values between SOS patients who would benefit from drug treatment versus those who do well with supportive care.
- 2.4 Quantify relative ability of CEUS parameters versus grayscale and Doppler ultrasound

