3.3 The long-term goal of our research is to accurately identify SOS patients who would benefit from defibrotide treatment using US SWE. The overall objective of this study is to validate SWE as an early diagnostic marker for SOS. Our central hypothesis is that SWE changes will precede clinical and conventional US diagnostic criteria for SOS. Our hypothesis has been formulated on the basis of our own preliminary data. We completed the first prospective cohort trial demonstrating that US SWE provides SOS diagnosis (80% sensitivity and 67% specificity) nine days earlier than current clinical criteria (9). SWE is widely available, has no known side effects, and is easy to learn and interpret. Our study enrolled 25 high-risk BMT patients over 18 months (five with SOS and two with severe SOS). More data is needed to determine the optimal window for testing to balance between improved test characteristics and early detection of disease. We propose conducting a prospective cohort study with 80 additional patients, 12 of which will likely develop SOS (including four with severe SOS) to optimize SWE timing. This study will increase the confidence in the findings from our preliminary study and allow us to test SWE against newly published clinical criteria. The rationale for the proposed research is that, if SWE can diagnose SOS earlier than clinical criteria, then SWE can guide early initiation of SOS treatment.

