### 6.2 Describe:

- There are no known risks to medical ultrasound imaging.
- CEUS Lumason® (sulfur hexafluoride lipid type-A microspheres) will be obtained through IDS pharmacy and administered through an already existing IV catheter by an RN or a radiology technologist trained and certified to administer the Lumason® contrast agent, and an abdominal ultrasound will be completed.
- Lumason (sulfur hexafluoride lipid-type A microspheres) is the investigational product. The recommended dose of Lumason for children is 0.03 mL/kg up to a maximum dose of 2.4mL injected into a peripheral intravenous catheter. See individualization of dose below.
  - 1. Follow the Lumason injection with a flush of 5 ml of 0.9% Sodium Chloride Injection, USP.
  - 2. The maximum total dose for children as listed in the package insert should not exceed 2.4 mL in any 10-minute period. With a maximal total dose of 4.8 mL in any one patient during a single exam.

- 6.3 Protected health information (PHI) to be collected for the purpose of this study alone will include; MRN, date of transplant, dates of ultrasound exams (attached data collection sheet). This information will be documented in RedCap. Within RedCap, there will be two separate files. One file will include minimal PHI (dates of service) and contain study data according to an assigned study ID number. The second file, will contain a master list of subjects linking the subject PHI with the assigned study ID number. The research record generated will consist of an excel spreadsheet from the data dictionary within RedCap. Security measures include: storage of the data on a password protected computer in a restricted assess departmental folder limited to only study personnel.
- 6.4 Participants in this study have two options regarding data collection, they may consent to take part in the CIBMTR Research Database or they may take part in only this study.

Data Collection Procedures for those that consent to take part in the CIBMTR Research Database:

Subjects may have already consented to take part in the CIBMTR Research Database (IRB# 11120281). If they are not yet taking part in that study, they will be given the option to consent for CIBMTR Research Database at the time they are consenting for this study.

If a subject chooses to take part in the CIBMTR database, data entered as part of this protocol will be entered into the CIBMTR database at the end of local site enrollment.

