Data will provided to CIBMTR in the form of a spreadsheet and will be password protected and sent to CMH only for data analysis.

Clinical and outcome data, including DOB, dates of service, exams, lab values and clinical timepoints will be evaluated.

Data Collection Procedures for those that do not consent to take part in the CIBMTR Research Database:

For subjects that consent to BMT Elastography (Internal) study, but do not consent to have their data entered into the CIBMTR database will have their clinical variables entered into a local REDCap database. Those data points will include DOB, dates of service, exams, lab values and clinical timepoints

Data Collection Procedures for both groups:

Additional clinical variables (not captured in the CIBMTR database needed to define our objectives) and elastography variables will be retrospectively extracted from the patients' electronic medical records and entered into REDCap. We will collect a number of variables based on the CIBMTR +100 Day outcome form and we will collect variables related to the modified Seattle criteria,

Baltimore criteria and the new EBMT criteria. We will also collect clinical and laboratory parameters of liver disease to help us evaluate for other hepatic complications from HCT. We will use the adult and pediatric EBMT criteria to determine the date on which the patient was first diagnosed with SOS. The date of diagnosis will be the first day on which the patient meets the EBMT criteria for their cohort (adult or pediatric). We will also use clinical data to grade SOS severity, to detect other hepatic complications from HCT, and to inform our SOS predictive modeling. For SOS grading, the day on which the patient meets the severity criteria for that particular grade will be recorded.

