- 20.6 Consented subjects will be provided a printed calendar outlining their research ultrasound schedule at the time of admission for the duration of their enrollment in the study. Each calendar will be specific to each subject's treatment and clinical course, which is being performed as standard of care.

For subjects that are enrolled in additional research ultrasound studies, all research ultrasound exams will be listed on the same calendar.

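### Section 6.1 puts suspicion-triggered SWE exams into the analysis without limit, so for objectives 2.1 and 2.2 the timing of some exams follows the emerging outcome

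*Protocol*

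**What the plan says.** Protocol Section 6.1, under Ultrasound Examinations and Timeline, sets the routine schedule: "Patients will undergo limited abdominal US with Doppler, CEUS and SWE once a week upon admission for conditioning", continuing to day +30 or discharge. Table 3 repeats the weekly frequency. The same section then adds exams that the clinical team orders "when patients have clinical suspicion for SOS and we will include these exams in our analysis". It names no objective to which this inclusion is limited.

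Two objectives in Section 2.0 depend on when exams take place. Objective 2.1 is to "establish optimal timing to test for SOS using SWE". Objective 2.2 is to "Determine if SWE can provide earlier SOS diagnosis compared to clinical criteria". The clinical side of that comparison is fixed in Section 6.4: "The date of diagnosis will be the first day on which the patient meets the EBMT criteria for their cohort".

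Three further places bear on the point. Section 3.3 expects 80 patients, "12 of which will likely develop SOS", and reports from the preliminary study 80% sensitivity, 67% specificity and a nine-day lead over clinical criteria. Section 9.1 blinds clinicians to SWE results. Section 6.1 says that the sonographer and radiologist are not blinded to clinical status.

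**The concern.** Weekly exams are timed by the calendar. Triggered exams are timed by a clinician's impression that SOS is developing, and that impression comes from the same clinical picture that will shortly satisfy, or fail to satisfy, the EBMT criteria. Pooling the two kinds of exam has a different consequence for each objective.

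- **Objective 2.1.** Exam timing is the quantity under study. A positive scan obtained because SOS was already suspected says nothing about whether a scan on a fixed schedule would have caught it.
- **Objective 2.2.** The comparison is SWE against clinical criteria. A triggered positive carries clinical suspicion over to the SWE side, so part of any apparent lead may belong to the clinicians.

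Blinding clinicians to SWE results does not remove this, because suspicion, not the SWE value, prompts the exam. With few SOS cases expected, a handful of such exams could matter.

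**Working it through.** The plan gives no figure for this point, so there is none to reproduce. The check has three steps.

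**1. Weight of one patient.** With 12 expected SOS cases (Section 3.3), one patient is 1/12 = 8.3 percentage points of sensitivity.

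**2. Closed-form illustration.** Assumptions, none from the protocol except the weekly interval: SWE becomes abnormal L days before the EBMT date; an exam after that point is always positive; weekly exams fall at random phase; one added exam takes place g days before the EBMT date, with g no larger than L; a patient is positive on any positive exam.

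- Weekly exams only: the first positive comes U days after onset, with U uniform on 0 to 7. The share positive before diagnosis is min(L/7, 1). Mean lead over all SOS patients is L − 3.5.
- With the added exam: every patient is positive before diagnosis. Mean lead is g + (L − g)²/14 when L − g is at most 7, and L − 3.5 otherwise.

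For g = 2:

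| L (days) | Positive before diagnosis, weekly only | With added exam | Mean lead, weekly only | With added exam |
|---|---|---|---|---|
| 3 | 3/7 = 43% | 100% | −0.5 | 2 + 1/14 = 2.1 |
| 5 | 5/7 = 71% | 100% | 1.5 | 2 + 9/14 = 2.6 |
| 7 | 100% | 100% | 3.5 | 2 + 25/14 = 3.8 |
| 9 | 100% | 100% | 5.5 | 5.5 |

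The effect is large for a lead of a few days and vanishes at nine.

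Mean lead among patients detected before diagnosis can go either way. With L = 3 and weekly exams only, detected leads are uniform on 0 to 3, with mean 1.5 days. An added exam at g = 1 gives 1 + 4/14 = 1.3 days, a fall. At g = 2 it gives 2.1 days, a rise. The fall arises because the added exam brings in patients with short leads.

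**3. Imperfect exams.** A simulation used per-exam sensitivity 0.8 (borrowing the 80% in Section 3.3, whose unit is not stated), lead SD 3 days floored at zero, EBMT date on days 7 to 20, no false positives, and triggered exams additional to the weekly ones. Illustrative results for positivity before diagnosis:

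- Mean lead 6 days, half of SOS patients triggered one day before diagnosis, within-patient correlation 0.5: 57.5% to 70.9%, or 0.134 × 12 = 1.6 cases.
- Mean lead 3 days, every patient triggered one day before, no correlation: 31.5% to 66.1%, or 0.346 × 12 = 4.2 cases. This is a deliberately extreme corner.
- Mean underlying lead about 12.5 days, which weekly exams would observe as between eight and nine days: a gain of about 8 points or less, or 0.08 × 12 = 0.96 of a case, even with every patient triggered.

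The last line matters because Section 3.3 reports an observed lead. Matching it to an underlying lead of 12.5 days assumes that the preliminary study scanned roughly weekly, and its schedule is not shown.

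Specificity is not sized here. Under an any-positive rule, extra exams in patients without SOS can only lower it or leave it unchanged, but Section 3.3 does not say whether its 67% is per exam or per patient.

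**The case against.** **The analysis plan may settle this.** Handling of scheduled and unscheduled exams is often left to a statistical analysis plan, and the one for this trial is not shown. That stands in part: such a plan could make scheduled exams primary, and the planned data would permit it. But the protocol is not silent. It states an unlimited inclusion, and a later document would have to narrow that sentence. A reader might go further and infer that the primary analyses of 2.1 and 2.2 are committed to pooling. The text does not say so; it only leaves pooling open.

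**The exams can be told apart anyway.** A reader might infer that the protocol offers no means of separating them. It does not support that. Section 6.3 records "MRN, date of transplant, dates of ultrasound exams (attached data collection sheet"), and that sheet is not available here. Section 20.6 gives each subject a "printed calendar outlining their research ultrasound schedule". Section 20.2 limits the Research PACS to exams done for research, and Section 6.1 has the clinical team order the suspicion exams. Together these give a plausible route, though no explicit scheduled-or-triggered flag is described.

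**Triggered exams might displace weekly ones.** This is tempting, since a displaced exam could delay or lose a first positive. Section 6.1 and Table 3 require weekly SWE with no such exception, so the plain reading is that triggered exams are additional.

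**The direction is not certain.** This stands. It depends on an any-positive rule that the protocol never states. The only quantified comparison, in Section 28.1, is mean change from baseline at day +5, and extra exams near diagnosis would affect a landmark of that kind much less. It would also be wrong to say that triggered exams necessarily lengthen the apparent lead.

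**The preliminary lead is long enough to make this moot.** If nine days holds, the effect is indeed small. But that lead came from a cohort with five SOS cases, and it is what this study sets out to test.

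**Conclusion.** The concern holds as a design point about objectives 2.1 and 2.2. A stated, unlimited inclusion rule lets the emerging clinical picture set the timing of some SWE exams, and positives found that way do not measure what weekly testing would detect. Given an any-positive rule, positivity before diagnosis can only rise or stay the same, while mean lead can shorten or lengthen.

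The documents do not determine the size. It is zero if no triggered exam precedes the EBMT date or if none changes a patient's result. It is small if the observed lead is near nine days. It could reach several of the 12 expected cases if the true lead is only a few days and most patients are triggered. The number and timing of triggered exams are assumptions throughout, so the figures above illustrate the mechanism and are not a forecast of bias. This is worth correcting because the correction is cheap; it does not invalidate the design.

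**What to change.** In Section 6.1, state that the primary timing, sensitivity and lead-time analyses for objectives 2.1 and 2.2 use only protocol-scheduled exams, and that a sensitivity analysis adds the clinically triggered ones. Say that triggered exams may still be used for 2.3 and 2.4. Flag each exam in REDCap as scheduled or clinically triggered, preferably when it is done; clinical orders and the Research PACS already offer a way to fill in the flag.

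The cost is one sentence and one data field. A few data points near diagnosis leave the primary analysis, which is felt with about 12 SOS cases, but they return in the sensitivity analysis and no data are discarded.

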# 7.0 Data and Specimen Banking

7.1 N/A

8.0 Genetic Analysis Information 8.1 N/A

# 9.0 Sharing of Results with Subjects

- 9.1 US SWE results will be blinded from clinicians and patients.
- 9.2 Any unexpected findings will be communicated to the ordering physician by [name] via phone or email.

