### **17.0** Risks to Subjects

17.1 We do not anticipate any additional risks to this study as all patients will already have IV access per SOC for BMT and no additional line placements will be required as part of this study. All subjects will be monitored during the Lumason CEUS examination by radiology personnel and by BMT staff after the exam for any adverse events.

Reported risks related to Lumason administration include:

Serious cardiopulmonary reactions, including fatalities, have occurred uncommonly in adults during or shortly following administration of ultrasound contrast agents, including Lumason. These reactions typically occurred within 30 minutes of administration. Hypersensitivity reactions such as skin erythema, rash, urticaria, flushing, throat tightness, dyspnea, or anaphylactic shock have uncommonly been observed following the injection of Lumason. The exclusion criteria eliminate any subjects with a known cardiac abnormality or a known sensitivity to sulfur hexafluoride, so we do not anticipate that these reactions will occur. Resuscitation personnel and equipment will be available during the study treatment and follow-up period.

Adverse Reaction	Number	(%)
Any Adverse Reaction	340	5
Headache	65	1
Nausea	37	0.5
Dysgeusia	29	0.4
Injection site pain	23	0.3
Feeling hot	18	0.3
Chest discomfort	17	0.2
Chest pain	12	0.2
Dizziness	11	0.2
Injection site warmth	11	0.2

17.2 This study poses a minor increase over minimal risk as it does not hold the prospect of direct benefit for the individual subject, but the

intervention presents an experience that is reasonably commensurate with those inherent to the subject's medical situation and is likely to yield generalizable knowledge about the disorder which is of vital importance to the detection of VOD/SOS. Physicians will be blinded to the results of the imaging.

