# 22.0 Provisions to Protect the Privacy Interests of Subjects

- 22.1 Privacy interests for subjects will be maintained by limiting interaction with subjects and LAR to only study personnel at the discretion of the treating physician.
- 22.2 This study is voluntary, the physicians involved do not have any financial gain or interest with the study. Subjects may withdraw participation at any time and their care and treatment at CMH will not be compromised. Subjects and their families will be told that there participation is voluntary and that they may stop at any time.
- 22.3 Only IRB approved members of the study team will be granted access to the study folder located on the network drive or the REDCap database. Additionally, study team members who are responsible for collected data only will be granted limited access to REDCap, allowing them to record data only.
- 22.4 PHI to be accessed and/or recorded for this research study includes: DOB, MRN, dates of service (US SWE exams, conditioning regimen, HSCT, lab dates and dates of severity milestones and death of applicable) will be recorded.
- 22.5 HIPAA authorization will be wrapped into permission/assent/consent form.

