# 29.0 Multi-Site Research

*29.1* Study-Wide Number of Subjects: 80

29.2 Study-Wide Recruitment Methods: CMH will be the only site recruiting subjects. The University of Washington – Seattle's involvement is to provide imaging consulting. [name] will have access to our PACS system for evaluation of the imaging for analysis and image protocol validation.

- All required approvals (initial, continuing review and modifications) will be submitted to CMH IRB (IRB of record) for approval and letter of correspondence provided by CMH IRB will be sent to each site for local IRB (relying IRB) approval. Each site will be required to send documentation of local IRB approval.
- All modifications will be communicated to sites and approved (including approval by the site's IRB of record) before the modification is implemented.
- All engaged participating sites will safeguard data, including secure transmission of data, as required by local information security policies.
- All local site investigators conduct the study in accordance with applicable federal regulations and local laws.
- All non-compliance with the study protocol or applicable requirements and any unanticipated problems will be reported in accordance with local policy.
- *29.3* Describe the method for communicating to engaged participating sites:
  - All education and training to researchers and research staff will be provided by CMH and documentation of training will be recorded.
  - All reportable events must be communicated within 5 business days of notification of reportable event to CMH study staff for submission to CMH IRB (IRB of record).
  - Interim results will be communicated through virtual meetings and electronic communication as they become available.
  - The closure of a study will be communicated through electronic documentation of correspondence letter from IRB of record to participating sites for relying IRB documentation.
  - •

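### SOS date and grade are assigned, and stored images evaluated off-site, with no stated masking, although unmasked status is unavoidable only at the bedside

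*Protocol*

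**What the plan says.** **Index test.** Protocol 6.1, under Ultrasound Examinations and Timeline, states: "By necessity, the sonographer and interpreting radiologist will not be blinded to the clinical status of the patient". The velocities are placed by the sonographer during the scan: "Twelve shear wave velocity measurements will be taken 2-3 cm below the liver capsule at the mid-clavicular line in the right hepatic lobe", with twelve more in the left lobe. Scans ordered by the clinical team on suspicion of SOS also enter the analysis: "The clinical team will order US, CEUS and SWE exams when patients have clinical suspicion for SOS".

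**Reference standard.** Under 6.4, the diagnosis date is the day the patient first satisfies the adult or pediatric EBMT criteria, and the day each severity grade is reached is recorded. The section describes this as the study team's own work. It also says that additional clinical variables and "elastography variables will be retrospectively extracted from the" patients' electronic records, with both entered into REDCap. No one masked to SWE is named for dating or grading.

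**Masking that is in place.** Section 9.1 says "US SWE results will be blinded from clinicians and patients", and 17.2 repeats the point: "Physicians will be blinded to the results of the imaging".

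**Resources already named.** Under 29.2 an outside imaging consultant has "access to our PACS system for evaluation of the imaging for analysis and image protocol validation". Under 22.3, team members who only collect data are "granted limited access to REDCap, allowing them to record data only". Neither arrangement is given a masking purpose.

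**The concern.** The central hypothesis (2.1, 3.3) is that SWE changes come before clinical and conventional ultrasound criteria. The main quantity is therefore an interval between two dates: when SWE becomes abnormal and when clinical criteria are met. If the person fixing one date knows the other, the interval can drift toward what the study hopes to show.

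The protocol accepts knowledge of clinical status when images are acquired and read, and is silent on knowledge of SWE when SOS is dated and graded. The same silence affects objective 2.3, which compares SWE values between SOS patients who would benefit from drug treatment and those who do well with supportive care, because the severity grade is assigned under the same arrangement. With about 12 SOS cases expected, a few judgement calls carry weight.

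**Working it through.** No figure in the protocol rests on masking, so the main check sets the sections side by side.

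**1. Who is masked to what**

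| Role | Masked? | Source |
|---|---|---|
| Treating clinicians, patients | Yes, to SWE | 9.1, 17.2 |
| Sonographer, interpreting radiologist | No, they know clinical status | 6.1 |
| Study team assigning EBMT date and grade | Not stated | 6.4 |
| Outside imaging consultant | Not stated | 29.2 |

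The first row protects the record from which criteria are later read. The last two rows are open.

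**2. How far necessity reaches.** A sonographer scanning an inpatient cannot avoid seeing the patient, so the argument holds for acquisition. It does not carry over to applying EBMT criteria to recorded clinical data, or to evaluating images already stored in PACS. Both are done away from the bedside and can be ordered and coded.

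**3. Whether separation is already implied.** Section 6.1 says ultrasound and clinical data are collected weekly in REDCap; 6.4 says extraction is retrospective. The two should be reconciled. On the weekly reading, SWE values could already be in the database when date and grade are assigned. On the retrospective reading, both kinds of data come from the same record. Section 22.3 limits some staff to recording data but does not separate clinical from SWE fields.

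**4. Size on lead time.** Inputs from 3.3: 12 expected SOS cases and a preliminary lead of nine days. The number of dates moved, *k*, and the days moved, *d*, are assumptions, all in one direction.

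Shift in mean lead time = *k* × *d* / 12

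- *k* = 3, *d* = 2: 6/12 = 0.5 day, and 0.5/9 = 5.6% of nine days
- *k* = 3, *d* = 3: 9/12 = 0.75 day, 8.3%
- *k* = 4, *d* = 3: 12/12 = 1.0 day, 11.1%

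**5. Size on sensitivity.** One SWE result that flips in a fixed set of 12 cases moves sensitivity by 1/12 = 8.3 points. Removing a case from the SOS group also changes the denominator. Starting from an illustrative 10/12 = 83.3%, the result is 9/11 = 81.8% (down 1.5 points) or 10/11 = 90.9% (up 7.6 points). These figures show how coarse a 12-case estimate is. They do not estimate bias.

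**6. What a full masked re-read would involve.** One screening scan plus at least four weekly scans to day +30 (30/7 = 4.3) is 5 per patient, and 5 × 80 = 400 scans if nobody is discharged early. Scans during conditioning and on suspicion would add to that.

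**The case against.** **The reference standard is already protected.** Clinicians and patients are blinded to SWE, and the revision history shows that blinding clinicians was a deliberate change. This largely stops SWE from shaping the weights, laboratory values and examinations behind the criteria. A reader might infer from 6.1 alone that index test and reference standard each influence the other freely; 9.1 and 17.2 do not support that. Some gaps remain. Unexpected findings go to the ordering physician (9.2). Clinicians themselves order SWE on suspicion. SWE values are taken from the medical record without a statement of how they are hidden there. Ascites may be radiographic in the listed Seattle and Baltimore criteria (the EBMT components are not listed).

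**Nothing says one person handles both kinds of data.** Correct. A reader might infer that whoever dates SOS has the SWE values in view, but 6.4 gives neither the extractor's role nor the order of work. The date also follows a fixed rule, which limits judgement without removing it. The point is only that no separation is stated.

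**Abstraction details may sit in a SAP or manual.** Possibly, and neither is shown. But the protocol itself decides who is unmasked in 6.1 and how date and grade are set in 6.4, so the safeguard belongs beside those statements.

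**Acquisition bias cannot be undone later.** This stands. Site, depth and number of measurements are prespecified, and before criteria are met the sonographer can know only of suspicion, not of a diagnosis. Evaluating stored images with status hidden does not repair biased placement, and a re-read of every scan would not be cheap.

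**Conclusion.** The concern holds in a limited form. Acquisition and on-site reading are unmasked by the protocol's own statement, which is plausibly unavoidable at the bedside. Dating and grading of SOS, and the consultant's evaluation of stored images, have no stated masking, and for these the necessity argument does not apply. Both sides of the lead-time comparison are therefore open to a review bias that could be reduced at little cost.

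The size of that bias is unknown. Under the assumed movement of 3 of 12 dates by 2 to 3 days, mean lead time shifts by 0.5 to 0.75 day, which is small against nine days and does not by itself threaten the lead-time conclusion. The 8.3-point step in sensitivity reflects the sample size and should not be read as bias. The case for changing the text rests on the low cost of the safeguard and on where it acts, the study's main question, and not on a demonstrated distortion.

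**What to change.** **Section 6.4.** State that EBMT date and severity grade are assigned from clinical fields alone, by an existing team member without access to the SWE fields, and are locked in REDCap before SWE values are opened or linked. Reconcile the weekly collection in 6.1 with the retrospective extraction in 6.4 so that the order of work is clear.

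**Section 29.2.** State that the consultant's existing evaluation is done on coded images with clinical status and transplant day hidden. No additional reader and no full re-read is needed.

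**Section 6.1.** Confine the necessity statement to bedside acquisition and on-site reading, and say that this unmasked step will be reported as a limitation.

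**Cost.** REDCap access rights, a fixed order of data work, and some effort to code images, since 20.2 says research PACS data are identifiable. Sample size, visits and patient procedures do not change. Bias in bedside acquisition is not removed.
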